10.2 Social and psychological risks

There is a social/psychological risk in this study of breaching confidentiality and having a patient's diagnosis discovered. The likelihood of this occurring is very low, and will be further lowered by creating a database that does not link patients' identity with their clinical data. Loss of confidentiality is a potential risk. However, except when required by law, patients will not be identified by name, social security number, address, or any other personal identifier.

10.3 Testing risks

The only study-related testing risks will be those of a venous blood draw, which involves minor bleeding (rare) and infection (extremely rare) at the puncture site.

10.4 Potential benefits to study participants

The hypothesis being tested is that alirocumab will be well tolerated when initiated in the inpatient setting during an acute MI, and that it will be effective in further lowering LDL-C levels in addition to standard of care, possibly with the additional effect of attenuating the inflammatory response during acute myocardial infarction. There is no guarantee, however, that there is a benefit of using alirocumab in the setting of acute myocardial

infarction. There is however, also, no guarantee that the subject will receive alirocumab as 50% of subjects will receive placebo. Finally, we also cannot exclude the possibility, although highly unlikely, that alirocumab will provide harm in the investigated population. In the ODYSSEY Long-Term analysis, indeed, fewer patients experienced an acute myocardial infarction on alirocumab vs placebo (0.9% vs 2.3%, $P=0.01$), and there is no evidence suggesting that the patients who experienced an acute myocardial infarction while on alirocumab had a worse outcome than those on placebo, as shown by a trend toward reduced cardiac mortality with alirocumab (0.3% vs 0.9%)⁵.

11) ASSESSMENT OF SAFETY

Safety parameters will include data deriving from history and physical examination performed at each encounter, laboratory data, and results of functional and imaging tests obtained as part of standard clinical care. The patient will be encouraged to contact the research team at any time with any concern or change.

Disease-related data will be assessed including change in symptoms (or new symptoms), change in functional capacity, vital signs, and significant changes in medications.

Data specific to the treatment will also be assessed. The patient will be asked about symptoms. Changes to treatment for side-effects or unanticipated problems will be performed without breaking the randomization code, unless deemed necessary for the treatment of the individual patient by the physician caring for him, in which case the physician will be made aware while the remainder of the team, especially the investigators performing and interpreting the tests, will be maintained blinded, if possible.

The risks of the tests performed have been described above. In order to reduce risk, the procedures will be performed by skilled practitioners in the standard clinical fashion.

11.1 Reporting of Adverse Events

An adverse event (AE) is any untoward medical occurrence in a clinical study subject administered a medicinal (investigational or non-investigational) product. An AE does not necessarily have a causal relationship with the treatment. An AE can therefore be any unfavorable and unintended sign (including an abnormal finding), symptom, or disease temporally associated with the use of a medicinal (investigational or non-investigational) product, whether or not related to that medicinal (investigational or non-investigational) product.

The occurrence of an AE may come to the attention of study personnel during study encounters and interviews of a study recipient for medical care, or upon review by an investigator and/or study coordinator. **All events considered AEs including local and systemic reactions will be recorded on the appropriate AE form.** Information to be collected includes event description, time of onset, clinician's assessment of severity, relationship to study intervention (assessed only by those with the training and authority to make a diagnosis, which would include a physician) and time of resolution/stabilization of the event. All AEs occurring while on study must be documented appropriately regardless of relationship. All AEs will be followed to adequate resolution. All AEs must be graded for severity and relationship to study product.

Severity of Event. All AEs will be assessed by the clinician as:

- Mild: events require minimal or no treatment and do not interfere with the daily activities.
- Moderate: events result in a low level of inconvenience or concern with the therapeutic measures. Moderate events may cause some interference with functioning and may require local or systemic drug therapy.
- Severe: events interrupt a patient's usual daily activity and will likely require systemic drug therapy or other treatment. Severe events are usually incapacitating.
- Life threatening: any adverse drug experience that places the patient or subject, in the view of the investigator, at immediate risk of death from the reaction as it occurred (it does not include a reaction that had it occurred in a more severe form, might have caused death).

Relationship to the intervention. All suspected AEs must have their relationship to study intervention assessed using the terms: associated or not associated.

- Definitely related: The event is temporally related to the administration of the study intervention and, in the opinion of the investigator, no other etiology explains the event.
- Probably related: The event is temporally related to the administration of the study intervention and represents, in the opinion of the investigator, the most plausible explanation of the event.
- Possibly related: The event is temporally related to the administration of the study intervention but, in the opinion of the investigator, it does not represent the most likely explanation of the event.
- Definitely Unrelated: The event is temporally independent of study intervention and/or the event appears, in the opinion of the investigator, to be explained by another etiology.

An **unexpected event** means an event, the nature or severity of which is not consistent with the applicable product information. An expected adverse drug reaction with a fatal outcome should be considered unexpected unless the local/regional product labelling specifically states that the event might be associated with a fatal outcome.

A serious adverse event (SAE) is any adverse event/experience occurring between baseline assessments and the patients final study visit that results in any of the following outcomes and is considered by the investigator(s) to be unexpected or not consistent with the natural history of the disease:

- Death;
- Life threatening (subject at immediate risk of death);
- Requires inpatient hospitalization or prolongation of existing hospitalization;
- Results in a persistent or significant disability or incapacity;
- Is a congenital anomaly/birth defect;
- Important medical events that may not result in death, be life threatening, or require hospitalization may be considered SAEs when, based upon appropriate medical

judgment, may jeopardize the subject and may require medical or surgical intervention to prevent one of the outcomes listed in this definition.

For reports of hospitalization, it is the sign, symptom or diagnosis which led to the hospitalization, that is, the serious event for which details must be provided.

Any event requiring in-patient hospital admission (or the prolongation of hospitalization) must be reported as a SAE.

Admissions to the hospital that do not meet the criteria for SAE reporting are:

- Social reasons, e.g. overnight stay because of distance between home and hospital
- Surgery or procedure planned and documented prior to entry into the study

All serious adverse events that have not resolved by the end of the study, or that have not resolved upon discontinuation of the subject's participation in the study, must be followed until any of the following occurs:

- The event resolves
- The event stabilizes
- The event returns to baseline, if a baseline value/status is available
- The event can be attributed to agents other than the study drug or to factors unrelated to study conduct
- It becomes unlikely that any additional information can be obtained (subject or health care practitioner refusal to provide additional information, lost to follow-up after demonstration of due diligence with follow-up efforts)

Adverse Event of Special Interest (AESI): An adverse event of special interest (AESI) is an adverse event (serious or non-serious) of scientific and medical concern specific to the investigational medicinal product (IMP), for which ongoing monitoring and rapid communication by the Investigator to the Marketing Administration Holder (MAH) may be appropriate. Such events may require further investigation in order to characterize and understand them. AESIs may be added or removed during a study by protocol amendment.

For this study, the AESI are:

- Increase in alanine aminotransferase (ALT):
 - ALT >3 x the ULN unless associated with aspartate aminotransferase (AST) increase (AST>ALT) and clearly attributed to cardiac cause.
- Allergic events.
 - Allergic drug reactions and/or local injection site reactions deemed to be allergic by the Investigator (or have an allergic component), that require consultation with another physician for further evaluation of hypersensitivity/allergy as per the Investigator's medical judgment should be reported as an AESI.
- Pregnancy:
 - Pregnancy occurring in a female patient enrolled in the study will be recorded as a pre-specified AE with immediate notification in all cases, and IMP should

- be discontinued in all cases. It will be qualified as an SAE only if it fulfills the SAE criteria. The follow-up of the pregnancy will be mandatory until the outcome of the pregnancy has been determined.
- Pregnancy occurring in the female partner of a male patient included in the clinical trial: if permitted by the female partner and by local regulatory policies, it will be recorded as a pre-specified AE with immediate notification (SAE if it fulfills the SAE criteria), and pregnancy should be followed-up until the outcome has been determined.
 - Symptomatic overdose with IMP:
 - An overdose (accidental or intentional) is an event suspected by the Investigator or spontaneously notified by the patient (not based on systematic injection counts) and defined as at least twice of the intended dose within the intended therapeutic interval (ie, 2 or more injections are administered in <7 calendar days), to be reported using the Term “symptomatic OVERDOSE (accidental or intentional), indicating the circumstance in parentheses (eg, “symptomatic overdose [accidental]” or “symptomatic overdose [intentional]”). The patient should be monitored and appropriate symptomatic treatment instituted.
 - The circumstances of the overdose should be clearly specified in the verbatim.
 - Neurologic events:
 - Neurologic events that require additional examinations/procedures and/or referral to a specialist should be reported as an AESI. If the event does not require additional examinations/procedures and/or referral to a specialist, it should be reported as a standard AE.
 - Neurocognitive events
 - All neurocognitive events will be considered as AESI
 - **New Safety Finding** means any (other than reportable individual case safety report (ICSR)) safety issue that may require expedited reporting because providing information that may lead to a change in the known risk-benefit balance for the product and as mentioned, but not limited to, in the following regulatory texts: *Europe: Volume 9A of the Rules Governing Medicinal products in the European Union (September 2008) Section 4.1*; and *US: FDA: 21 CFR Parts 312 Investigational New Drug Application- Section 312.32, (c) (1) IND safety reports*.

Instructions:

- All Serious Adverse Events (SAEs) regardless of the relationship to a Regeneron/Sanofi product and all Adverse Events of Special Interest (AESIs) must be reported to Regeneron/Sanofi within 24 hours of becoming aware of the event

Reports by E-MAIL should be sent to: [contact] or [contact], within 24 hours of receipt by investigator/sponsor. E-Mail or Fax transmission should include the following:

Investigator-Sponsored (IST #) study number: _____

Study Title: _____

Name of Principal Investigator: _____

- The Sponsor must provide to Regeneron/Sanofi upon request, results of any relevant complementary exams performed to obtain the final diagnosis of any SAE or AESI (e.g. hospital discharge summary, autopsy, consultation).
- The sponsor shall be responsible for ensuring submission of required expedited and periodic reports to the appropriate Regulatory Authority (RA), the Ethics Committee and investigators of each country participating in the Investigator-Sponsored Study (ISS, based on applicable regulations).
- Any Periodic reports (e.g. Development Safety Update Report (DSUR)), submitted to Regulatory Authority must first be transmitted to Regeneron/Sanofi for review and comment
- The Sponsor must provide to Regeneron/Sanofi any New Safety Findings pertaining to safety of the Investigational product within one (1) business day (e.g. Data Safety Monitoring Board recommendations).

12) DISCONTINUATION OF STUDY PARTICIPATION AND WITHDRAWAL

Patients may withdraw from the study at any time. The patient can decide to forgo any study procedures that makes him/her uncomfortable or wish not to complete. The study doctor may however stop the participation of the patient in this study at any time for many reasons including (*but not limited to*) the study doctor thinks it is necessary for patient health or safety, the patient has not followed study instructions, or administrative reasons requiring withdrawal.

Loss to follow-up can occur due to patients' withdrawal or death. If patients are lost to follow up and their clinical condition cannot be established (alive vs dead, hospitalized vs not), they will be excluded from the initial analysis, and then reintroduced for sensitivity analysis considering all potential outcomes. A 10% attrition rate is a reasonable assumption.

13) STATISTICAL CONSIDERATIONS

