- Secondary Endpoints:** Placebo-corrected percentage change in calculated LDL cholesterol from baseline to 72 hours; placebo-corrected percentage change in PCSK9 levels from baseline to 72 hours and 14 days; placebo-corrected percentage change in lipoprotein(a) levels from baseline to 72 hours and 14 days; placebo-corrected percentage change in inflammatory markers (high-sensitivity CRP, IL-6, IL-10, and TNF- α) from baseline to 72 hours and 14 days; and safety and tolerability of alirocumab when initiated in the inpatient setting soon after an NSTEMI.
- Study Design:** Randomized, double-blinded, placebo-controlled phase IV clinical trial of a single dose of Alirocumab 150 mg or matched placebo in a 1:1 ratio. Patients will be assessed at enrollment, 72 hours and 14 days after treatment.

3) BACKGROUND INFORMATION AND SCIENTIFIC RATIONALE

Acute myocardial infarction (AMI) remains a leading cause of mortality and morbidity across the nation and worldwide. While major advances in reperfusion strategies over the past several decades have significantly reduced early mortality rates after AMI, patients who survive the index event are increasingly at risk for adverse cardiac remodeling and the sequelae of heart failure and sudden cardiac death¹. The aging population accelerates this problem, making heart failure a major public health concern. Heart failure, indeed, currently affects approximately five million Americans with increasing rates of prevalence and incidence.

Anticoagulants, antiplatelet agents, and neurohormonal blockers have become standard of care in the treatment of patients with AMI, given their established effects on mortality. Cholesterol-lowering drugs, primarily HMG-coA reductase inhibitors – statins – have been studied as a means not only to reduce LDL cholesterol (and hence the incidence of a first or recurrent AMI) but also as an adjunct to acute AMI therapy. In the MIRACL trial, atorvastatin 80mg was administered within 24 to 96 hours after presentation with acute coronary syndrome (ACS). When compared to placebo, the atorvastatin group had a reduction in the primary endpoint (composite of death, nonfatal AMI, cardiac arrest with resuscitation, or recurrent symptomatic myocardial infarction) from 17.4% to 14.8% (relative risk = 0.84 [0.70 – 1.00], p=0.048)².

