10.1 Alirocumab

Alirocumab is a PCSK9 inhibitor which has been shown to significantly lower LDL-cholesterol, both in patients with heterozygous familial hypercholesteremia (HeFH) and in patients without HeFH who have clinical atherosclerotic disease. It is subcutaneously administered by means of an auto-injector. Its safety and efficacy have been broadly investigated multiple clinical trials in patients with or without HeFH who are already on maximally tolerated statins, with or without additional lipid-lowering agents⁵⁻⁸. Patients in this study will similarly be required to have been on at least moderate-intensity statin therapy prior to presentation for acute MI, and they will receive a single dose of alirocumab 150 mg subcutaneously or placebo. There are no dose-adjustments needed based on age or weight. Drug-to-drug interactions are minimal and not expected to be clinically relevant.

Side effects have been reported with alirocumab. Adverse reactions recorded in the current reference document for alirocumab are: injection site reactions (including erythema/redness, itching, swelling, pain, tenderness), upper respiratory tract signs and symptoms (including mainly oropharyngeal pain, rhinorrhea, sneezing), pruritis, hypersensitivity, eczema nummular, urticarial, and hypersensitivity vasculitis.

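### The extra condition in the SAE definition either does almost nothing or contradicts the hospitalization rule and can leave out a cardiac death

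*Combined protocol and SAP*

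**What the plan says.** Four statements in Section 11.1 (Reporting of Adverse Events) bear on this point.

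- **Meaning of unexpected.** An unexpected event "means an event, the nature or severity of which is not consistent with the applicable product information". The next sentence adds: "An expected adverse drug reaction with a fatal outcome should be considered unexpected unless the local/regional product labelling specifically states" that a fatal outcome may occur.
- **SAE definition.** The paragraph that follows requires one of six outcomes, and also that the event "is considered by the investigator(s) to be unexpected or not consistent with the natural history of the disease".
- **Hospitalization rule.** Further down: "Any event requiring in-patient hospital admission (or the prolongation of hospitalization) must be reported as a SAE". Only two exceptions follow: stays for social reasons, and surgery or procedures planned and documented before entry.
- **What SAE status triggers.** The reporting instructions require SAEs, whatever their relationship to the product, and AESIs to reach the funders within 24 hours.

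Two other sections supply context. Section 3 describes survivors of an acute MI as "increasingly at risk for adverse cardiac remodeling and the sequelae of heart failure and sudden cardiac death". Section 10.1 gives the known reactions to alirocumab in a list that begins: "Adverse reactions recorded in the current reference document for alirocumab are: injection site reactions".

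**The concern.** A serious outcome alone does not make an event an SAE under this definition. The investigator must also judge the event unexpected, or out of keeping with the course of the disease. No sentence says whether *unexpected* here carries its defined meaning or means unexpected for a patient with NSTEMI. The natural-history wording beside it invites the second meaning.

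The choice matters because every patient has just had an infarction. If disease-consistent events are filtered out, the events removed are mainly cardiac, and cardiac harm from the drug could resemble the natural history of the disease. Safety and tolerability is a listed secondary endpoint (Section 4.3). Section 4.2 calls this the first trial of alirocumab in acute NSTEMI inpatients, and Section 10.4 accepts that harm cannot be excluded. The reporting instructions deliberately ignore causal relationship. A natural-history filter would bring attribution back one step earlier, because an event ascribed to the disease would never become an SAE.

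**Working it through.** The question is one of wording, and the plan gives no figure to reproduce. The check compares the sentences under each meaning of *unexpected*.

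**Set-up.** Take any event with one of the listed outcomes. Let L mean that it is listed in the product information, and N that it is consistent with the natural history of NSTEMI.

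**Reading A: unexpected as defined.** The event is an SAE if (not L) or (not N).

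**Reading B: unexpected for the disease.** Both limbs then test the same thing, so the event is an SAE only if (not N).

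| Event with a serious outcome | Reading A | Reading B |
|---|---|---|
| Not listed, not natural history | SAE | SAE |
| Listed, not natural history | SAE | SAE |
| Not listed, natural history (e.g. sudden cardiac death) | SAE | **not an SAE** |
| Listed and natural history | not an SAE | not an SAE |

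**Reading A, size of the excluded cell.** Only the last row is excluded. Section 10.1 lists seven reaction groups: injection site reactions, upper respiratory symptoms, pruritus, hypersensitivity, nummular eczema, urticaria and hypersensitivity vasculitis. None of the seven is cardiac, so the row is practically empty. The sentence on fatal reactions narrows it further. The condition therefore does almost nothing.

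**Reading B, conflict with the hospitalization rule.** A readmission for recurrent MI or heart failure is natural history, so the definition says it is not an SAE. The hospitalization rule says it must be reported as one, and neither exception applies. The two sentences cannot both hold.

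**Reading B, events that no other rule recovers.** Take a sudden cardiac death at home, or one during the index stay that does not lengthen it.

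- The hospitalization rule does not apply: there is no admission and no prolongation.
- The sentence on fatal outcomes does not apply: it concerns adverse drug reactions, not deaths from the disease.
- The AESI list does not name it. The six items are ALT increase, allergic events, pregnancy, symptomatic overdose, neurologic events and neurocognitive events; none names death or a cardiac event as a trigger. AESIs may be serious or non-serious, so a fatal allergic or neurologic event could still qualify.
- No other sentence makes every death an SAE.

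**Outcomes that depend on the reading.** Six are listed: death, life-threatening event, hospitalization or prolongation, disability or incapacity, congenital anomaly, and important medical event. Hospitalization has its own unconditional rule, and a congenital anomaly cannot be natural history of NSTEMI, so it is an SAE on both readings. That leaves 6 − 1 − 1 = 4 at most.

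**The case against.** The strongest reply is that the protocol already settles the meaning. The definition of *unexpected* stands immediately before the SAE paragraph, and on that meaning a cardiac death is an SAE. Reading B ignores the definition and makes the two limbs of the condition say the same thing. On Reading A each limb works: the first brings in disease events that are not labelled, and the second brings in labelled reactions that are not part of NSTEMI, such as serious hypersensitivity. An investigator facing a readmission also has a later, specific and unconditional instruction.

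This stands as far as it goes. Reading A is the better construction, and it is treated here as the default. But no sentence says which meaning governs the SAE definition, and none says outright that every death is an SAE. The natural-history wording has a practical effect only if it is read as a filter on disease events.

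It is also fair to say that four of six is a count of list items, not of patients. Important medical events already depend on medical judgement, and many life-threatening or disabling events would probably cause or prolong a hospital stay, although the documents give no rate. What mainly remains is a death without a qualifying hospitalization, among 20 patients followed for 14 ± 3 days.

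Finally, the separate expectedness field is not strictly needed to remove the ambiguity; a cross-reference to the definition would fix the meaning. It would, however, keep a condition that then excludes almost nothing.

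**Conclusion.** The concern holds, as a minor defect. On the default reading the condition is practically idle. On the disease reading it contradicts the hospitalization rule and can remove SAE classification, and with it the 24-hour report to the funders, from a disease-consistent death or other serious event that neither causes an admission nor prolongs a stay.

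The consequence is limited. The event would still be recorded and graded, and Section 11.1 adds: "All AEs will be followed to adequate resolution". The sponsor's regulatory and ethics reporting duties are unaffected, and no efficacy result changes. At most four of the six outcomes are involved, and the number of events cannot be derived from the documents.

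Two assumptions carry the conclusion. The harmful branch requires an investigator to read *unexpected* against the disease. The statement that the default reading excludes almost nothing takes the list in Section 10.1 to represent the applicable product information, because the full label is not part of the documents.

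**What to change.** Delete from the SAE definition the condition that the investigator must consider the event unexpected or inconsistent with the natural history of the disease. SAE status then follows from the outcome and agrees with the hospitalization rule. The item on important medical events keeps its own medical-judgement wording. Record expectedness as a separate field on the event form, using the product-information definition already in Section 11.1.

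The cost is a one-clause amendment, one form field and possibly a few more SAE reports in a 20-patient trial. If the default reading was intended, almost nothing is lost; if the other reading was possible, the contradiction and the gap both close.
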